6	Prolonged concurrent intake of any drug that is known to prolong QT interval on the ECG as per physician discretion and these drugs include anti-arrhythmic drugs, quinidine, chlorpromazine, haloperidol, olanzapine, thioridazine, fluoxetine, antibiotics belonging to quinolone and macrolide family, antibiotics, fenfluramine and other appetite suppressants, Beta-2 agonists, terfenadine and other antihistaminic drugs, liquorice and potassium lowering drugs
7	History of taking any kind of Ayurvedic formulation or any other form of CAM (Complimentary Alternative Medicine) therapy in the preceding 2 months
8	Unwilling to come for regular follow-up for the entire duration of the study.
9	Non – co-operative attitude of the participant
10	Any condition that, in the opinion of the investigator, does not justify the participant's inclusion in the study.

h Sample size: 400 (randomized sample size)

i Treatment and Follow up Monitoring Schedule:

This will be common to both the study arms

Visit - 1: Baseline Visit

Visit - 2: Week 4 Visit

Visit - 3: Week 8 visit

Visit - 4: Week 12 visit

Participants will be under the combined care of Modern medicine physician and Ayurvedic physician. The details of the procedures and investigations carried out at each visit are as mentioned in the Schedule of Events (Appendix A)

i. Concomitant medication:

Medication prescribed for other co-existent disease will continue under medical supervision which will be recorded in the case record form (CRF).

k Efficacy criteria:

The primary efficacy measure will be as follows:
(i)Proportion of SARS-CoV-2 infection* free participants
on completion of study (ii)Proportion of participants
contracting COVID-19 during the study period
The secondary measures of efficacy and safety will include proportion of
participants developing COVID-19, drug related adverse event, drug
tolerability, General Health Related Questionnaire (behavior, habit and
fitness/ HR-BHF), Quality of life (WHO QOL Brief), Ayurveda
measures, Immune Status (serology for specific anti SARS-CoV-2 IgM
and IgG antibodies)

- *The diagnosis of COVID-19 will be confirmed by a real time RT-PCR based diagnostic test on nose/mouth swab
- 1 Safety criteria: All adverse events occurring during the study will be recorded and monitored as per GCP-ICH guidelines. Safety would also be assessed in case of all withdrawals.
 - m. Laboratory investigations: These are common to the both the study arms

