- xiii. Physician decision that involvement in the study is not in the patient's best interest

j. Efficacy:

A) Primary Outcomes:

- a) Mean time (days) for clinical recovery [Day of randomization to the day of clinical recovery (see criteria below)]
- b) Proportion of patients showing 'clinical recovery'

Criteria of 'Clinical Recovery':

- i. Normal body temperature (≤36.6°C axilla or ≤37.2 °C oral)
- ii. Absence of cough or mild cough (infrequent, short episodic, non-wheezy, relieved by minimal or no medication, not interfering with routine speech and not related to lying in bed, mild sore throat or nasal congestion)
- iii. Absence of breathlessness on routine daily self-care chore or respiratory rate less than 30 breaths per minute without supplemental oxygen
- iv. Absence of any other symptom/sign attributed to COVID-19 illness
- v. Normalization of SpO2 by standard peripheral oximetry device (above 95 percent)
- vi. Recovery should be sustained for at least 48 hours under physician observation
- vii. Assessed by physician blinded to treatment allocation (blinded end-point assessment)
- viii. All of the above criteria ought to be fulfilled

Note: Clinical recovery would be deemed from the first day of satisfying the above criteria

B) Secondary Outcomes:

- 1) Rate of patients with negative SARS-CoV-2 on nasal or throat swab in a 2 day continuous real time RT-PCR test beginning from 'first day of clinical recovery' or 'Day 10 after onset of symptoms depending on whichever of the two time points is first achieved
- 2) Timelines (days counted from onset of illness)- normal body temperature, absence or minimal cough (see 'clinical recovery' for the definition), absence of dyspnoea, onset of clinical pneumonia, pneumonia diagnosed on chest X-Ray or CT scan, time to supplemental

oxygen, admit in intensive care unit, mechanical ventilation (non-invasive), mechanical ventilation (invasive), steroid use, respiratory failure, adult respiratory distress syndrome, cytokine storm syndrome, secondary infection, shock, septicaemia shock, hospital discharge, negative nose or throat swab confirmatory test, and all-cause mortality.

- 3) Proportion of patients developing an event that reflects clinical or otherwise improvement of worsening (the events are similar to those listed under Timelines, see above)
- 4) Improvement on pulmonary function tests using simple 'home expiratory spirometer' device and peripheral pulse oximetry

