- 5) Improvement in selected laboratory parameters: blood haemoglobin, differential and total leukocyte counts, liver enzymes, renal functions, acute phase reactants, serum IL-6 and other selected cytokines, serum muscle enzymes (CK, CPK), serum ferritin, serum d-Dimer, anti-oxidant markers, serum BNP (cardiac function)
- 6) Serological Protective Antibody Assay (IgM and IgG)
- 7) Radiological Improvement on digital chest X ray and HRCT chest
- 8) Drug related: side effects and toxicity, and tolerability (Safety criteria: All adverse events occurring during the study will be recorded and monitored as per GCP-ICH guidelines. Safety would also be assessed in case of all withdrawals.)
- 9) Health status: WHO QOL brief, health related behaviour habit and fitness questionnaire based on visual analogue scale

10) Ayurvedic Measures:

BASELINE:

- a) Prakriti
- b) Clinical Features
- c) Ayurvedic Disease Subsets / Stages

FOLLOW UP / MONITORING:

- a) Clinical Features
- b) Ayurveda examination
- c) Ayurvedic Disease Subsets / Stages

k. Medication*:

Interventional Experimental:

i)AYUSH-64: 500 mg tablet, 2 tablets bid (twice daily)

ii) Yashtimadhu: 300 mg tablet, 2 tablets bid (twice daily)

iii)Sanshamani Vati Plus: Each tablet to contain 300 mg Guduchi plus 75 mg Pippali, 2 tablets bid (twice daily) (*Considering the *Dosha* status Ayurveda physician may change the dose.)

Concomitant:

Medication prescribed for other co-existent disease and permitted as per inclusion criteria will continue under medical supervision of the primary care physician and this will be recorded in the CRF.

l. Laboratory investigations:

These are common to the each of the three Ayurveda formulation drug trials:

- i. Haemogram, Platelet count, Total leukocyte differential count, Hemoglobin and ESR,
- ii. Liver function test Serum Bilirubin, ALT, AST, Alkaline phosphatase,
- iii. Kidney Function Test (Serum creatinine, Blood Urea Nitrogen)
- iv. Lipid profile (Total cholesterol, HDL cholesterol, LDL cholesterol, Triglycerides, VLDL)
- v. Blood Sugar Level
- vi. Urine Routine
- vii. C-Reactive protein titer
- viii. LDH, Ferritin
- ix. Pro-Cal
- x. CK, B-type natriuretic peptide (BNP), Troponin, D-Dimer
- xi. Serum Electrolytes (Sodium, Potassium, Chloride, Iron, Zinc, Manganese) Vitamin D, B12
- xii. Oxidation Biomarkers-Superoxide Dismutase (SOD), Glutathoine (GSH)

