- xiii. Cytokine Panel (Interleukin-2, Interleukin 1 4, Interleukin-6, Interleukin-10, TNF-α, Interleukin-1β, Interleukin-13), Monocyte Chemotactic Protein (MCP), Gamma Interferon. RATIONALE FOR CYTOKINE ASSAY: Cytokine assay can be used to study important anti-viral effects (gamma interferon), immune mediated inflammation (IL-6, anti-TNF, IL-17), TH 1 and TH 2 immune response and antibody producing B cell activity (IL4, IL13), activation of immune cells such as macrophage activation (MCP). Intense up regulation and elevation of IL 6 and several other cytokines has been reported by several clinical case series and research in COVID-19 and can guide specific therapy (as in case of use of monoclonal antibody to IL-6 receptor being used to treat Cytokine storm in COVID 19)
- xiv. Serum Immune Response tests (IgG and IgM) for COVID-19
- xv. Urine Pregnancy Test for women of child bearing potential

Other Investigations:

- i. USG Abdomen and Pelvis
- ii. Color Doppler and 12 Lead ECG
- iii. Chest X-ray
- iv. HRCT Chest

m. Withdrawal Criteria

The patient can withdraw at any time during the study without assigning any reason. The investigator may also withdraw the patient due to reasons connected with the severity of disease, interventional drug (adverse event) or some protocol deviation. Detailed description is provided in the protocol.

n. Statistical statement:

The design of the drug trial is exploratory in nature. Though a randomized selection of patients will be done to either of the two arms, the sample size is that of convenience (expert opinion) and the same is not statistically powered however, sample size (70 patients in each arm) sufficient to draw meaningful conclusions. The statistical significance p<0.05(two sided) is predefined for analysis. Statistical analysis will be performed using standard tests to compare the two interventional arms for primary and secondary efficacy measures. Safety events will be also analyzed. Both intent-to-treat and per protocol completer analysis will be performed. Regression analysis will be done to identify predictors of response.

o. Regulatory clearances:

The protocol will be submitted for all regulatory and other relevant approvals including that of the ethics committee prior to beginning the clinical component of the study. The trial protocol will be registered under Clinical Trial Registry of India before enrolling the first patient.

p. Funding agency:

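### Both synopses name their adverse-event outcome as drug related, although the trials are open label and the adjunct control arm takes no Ayurvedic drug; the between-arm comparison should be defined regardless of causality

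*Protocol*

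**What the plan says.** **Adjunct synopsis.** Section j, B) Secondary Outcomes, item 8, opens with "Drug related: side effects and toxicity, and tolerability". A bracket in the same item continues "Safety criteria: All adverse events occurring during the study will be recorded and monitored as per GCP-ICH guidelines" and then "Safety would also be assessed in case of all withdrawals". The statistical statement (section n) adds "Safety events will be also analyzed" and does not define safety events. Secondary outcomes 2 and 3 include clinical events that need no causality judgement: the list in item 2 ends with "hospital discharge, negative nose or throat swab confirmatory test, and all-cause mortality", and item 3 is "Proportion of patients developing an event that reflects clinical or otherwise improvement of worsening".

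The study design (section f) is open label with a blinded end point. Blinded assessment is specified only as criterion vii of clinical recovery. The control is SOC alone, with 70 patients per arm. The primary objective covers safety as well as efficacy.

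**Prophylaxis synopsis.** The secondary measures in section k include "participants developing COVID-19, drug related adverse event, drug" tolerability. The safety criteria in section l state "All adverse events occurring during the study will be recorded and monitored as per GCP-ICH guidelines". The trial is open label, randomises 400 participants, and gives a study drug in both arms (hydroxychloroquine, HCQ, or Ashwagandha).

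**The concern.** Whether an event is drug related is a judgement, and in these trials it would be made by people who know the arm. In the adjunct trials the problem is structural. No event in the SOC arm can be related to an Ayurvedic drug that nobody there takes. A count of drug-related events is then either one-sided, or it depends on how readily sites blame SOC medicines in each arm.

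An outcome of this kind can err in both directions. Equal true event rates can appear as a difference. Harm from the study drug that is put down to COVID-19 or to co-medication drops out of the count. Because safety belongs to the primary objective of the adjunct trials, the outcome named for it should not rest on that judgement.

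**Working it through.** **1. Label against criteria.** In adjunct item 8 the label is causal and the bracket is not. In the prophylaxis synopsis, section k is causal and section l is not. In both, the all-event sentence speaks of recording and monitoring; it does not say which events are compared between arms. Adjunct section n applies the two-arm tests to primary and secondary efficacy measures. Item 8 stands in the list of secondary outcomes under the efficacy heading, so it can be read as one of the tested outcomes. The separate sentence on safety events can equally be read as moving safety elsewhere. The text does not settle which reading applies.

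**2. Illustration for the adjunct trials.** The documents give no adverse event rate and no share attributed to drug, so there is no figure of the plan to reproduce.
- From the documents: n = 70 per arm; two-sided significance level 0.05.
- Assumed: the same true adverse event rate r in both arms (20%, 30% or 40%); a share a_T of events called drug related in the drug arm (25% or 50%); a share a_C in the SOC arm (0% or 10%).
- Rates of the named outcome: p_T = r × a_T and p_C = r × a_C. For r = 30%, a_T = 50%, a_C = 10%: p_T = 15% and p_C = 3%.
- Chance of a nominal difference: the sum of Bin(i; 70, p_T) × Bin(j; 70, p_C) over all pairs (i, j) whose Fisher exact p-value is below 0.05.

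| True rate, both arms | All events | 25% vs 0% | 25% vs 10% | 50% vs 0% | 50% vs 10% |
|---|---|---|---|---|---|
| 20% | 0.031 | 0.137 | 0.042 | 0.713 | 0.362 |
| 30% | 0.033 | 0.429 | 0.103 | 0.962 | 0.624 |
| 40% | 0.032 | 0.713 | 0.170 | 0.997 | 0.806 |

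Columns 3 to 6 give the attributed shares, drug arm vs SOC. True harm is equal in every cell, so any excess over about 0.03 comes from attribution alone.

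A single data set shows the same effect. At 30%, each arm has 0.30 × 70 = 21 patients with an event, and 21/70 vs 21/70 gives Fisher p = 1.0. If about half of the drug-arm events (10) and none of the SOC events are called drug related, 10/70 vs 0/70 gives Fisher p = 0.0014.

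**3. Illustration for the prophylaxis trial.** Assume equal arms of 400/2 = 200 and a true rate of 20% in both, which is 40 participants each.
- 60% of events attributed under HCQ and 30% under Ashwagandha: 24 vs 12. Uncorrected chi-square p = 0.036; continuity-corrected p = 0.055; Fisher p = 0.053.
- 50% and 30%: 20 vs 12. Fisher p = 0.20.

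Here the result is borderline at most and turns on the choice of test.

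**The case against.** A reader who stops at the words drug related might infer that safety is restricted to such events, or that the safety objective cannot be answered. The documents do not support that:
- The bracket in adjunct item 8 and prophylaxis section l cover all adverse events.
- Adjunct section n analyses safety events with no drug-related limit.
- All-cause mortality, intensive care admission, ventilation, respiratory failure and shock are outcomes in their own right, free of attribution, so much serious harm would still be counted.

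All of this stands. It does not define the adverse-event comparison, however. Apart from death, those listed events mainly describe the course of COVID-19 and do not replace a count of adverse events from any cause.

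It is also fair to say that no sentence expressly commits the sponsor to a significance test of drug-related counts, and that adverse event tables usually belong in a statistical analysis plan, which is not shown here. Tabulation can indeed wait. The wording of a named secondary outcome is already fixed in these synopses.

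For the prophylaxis trial, a reader might infer a predictable bias against HCQ, because the background asks for diligent monitoring of HCQ and presents Ashwagandha through its benefits. That is conjecture about investigators. It is relevant that HCQ is taken for 7 weeks and Ashwagandha for 12, so the time in which an event can be attributed to current drug differs by arm. The documents establish neither the direction nor the size of any resulting bias.

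**Conclusion.** The point holds as a defect in how the adverse-event outcome is named, not as a gap in safety data. As worded, a between-arm comparison of that outcome would depend on attribution by people who know the allocation. The problem is clear in the adjunct trials, where the control takes no Ayurvedic drug, and weaker in the prophylaxis trial, where both arms take a study drug.

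Over the assumed range for the adjunct trials, the chance of a nominally significant difference with equal true harm runs from 0.04 to 0.997, against about 0.03 when all events are compared. These figures show the mechanism; they do not predict a result. They rest on assumed event rates and attribution shares, and the upper end requires that no SOC-arm event is ever called drug related. The correction should be made, since the outcome is stated and a better one can be built from data the protocol already collects.

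**What to change.** In adjunct section j, secondary outcome 8, and in prophylaxis section k, state that the between-arm safety comparison is the proportion of participants with any adverse event, and the proportion with any serious adverse event, regardless of causality, by randomised arm. Report investigator-assessed drug relatedness descriptively, as supportive information. This also removes the mismatch between the label and the all-event safety criteria beside it.

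The cost is one line in each synopsis. All adverse events are already to be recorded, so no new data, visits or participants are needed.

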The total duration of the study is 12 weeks – this includes a period of hospital based treatment followed by a post recovery period. The Ayurvedic drug will be prescribed as per protocol for a total duration of 12 weeks.

f. Study design:

This is a prospective, randomized, open label, blinded end point (PROBE), parallel efficacy, multicentric, two arm study to compare the efficacy of a combination of Standard of Care (SOC) plus a selected individual Ayurveda herbal drug (Samshamani Vati Plus or AYUSH 64 or Yashtimadhu) to SOC (active control). The Ayurveda drug is being considered as an adjunctive or an add-on therapy and each of the three drugs will be evaluated in separate two arm trial with a common study design. The drug trials are 'exploratory' in design. The Study Flow diagram summarizes the study design and schedule of events (Fig 1) (Appendix A).

- g. Sample size: The total sample size is 140 patients per drug trial- 70 patients in each arm.
- **h. Study Population:** All adult patients with laboratory-confirmed SARS-CoV2 infection with mild to moderate category will be selected from the outpatient or inpatient facility in COVID-19 medical centers/hospitals. Voluntary patients will be explained about the study and if willing will sign the informed consent and be screened for eligibility.

Screening of Voluntary and Consenting In-patients suffering from Mild to Moderately Severe COVID-19 for Eligibility as per Inclusion-Exclusion Criteria 3 Ayurveda formulation drug trial studies under a common protocol (Separate study for each AYUSH 64 / Yashtimadhu / Samshamai Vati Plus)

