Randomize Eligible Hospitalized Patients (Open Label, Parallel Efficacy, Active Control Standard of Care (SOC), Two Arm Study) Selected Ayurveda Formulation (Adjuvant) Versus SOC (Active Control) Time Points Clinical Assessment Investigations Case Record Form (CRF), Medical Diagnostic (PCR), Serology (IgM, IgG), History Clinical Examination, Ayurveda Baseline Routine Hematology Profile, Special Assessment, Health Status (WHOQs), Assays, X-Ray Chest & Imaging, ECG QoL (HR-BHF) Brief Clin Exam, Ayu Exam, Health Diagnostic (PCR), Serology (IgM, IgG), Week 4 Routine haematology Body Profile, Status (WHO-Qs) & QoL (HR-BHF Qs), Adverse Events (AEs) Special Assays Brief Clin Exam, Ayu Exam, Health Diagnostic (PCR), Serology (IgM, IgG), Week 8 Status (WHO-Qs) & QoL (HR-BHF Routine haematology Body Profile, Qs), Adverse Events (AEs) Special Assays Completion Outcome Assessment, CRF Diagnostic (PCR), Serology (IgM, IgG), Week 12 Clin Exam, Ayu Exam, WHO- Qs & Routine haematology Body Profile, QoL (HR-BHF Qs), AEs Special Assays

*Further Assessment Time Points: (i) During Hospitalization: Daily monitored vital parameters, disease symptoms, disease progression and recovery, and investigations carried out as per protocol till DISCHARGE; Laboratory and Imaging investigations as per protocol but the study investigator and treating physician can do any additional test as per their judgment (ii)Post DISCHARGE: Daily Telephonic Contact using a special mobile phone application for any relapse or any other symptoms or complications or any other Issue (iii) Discharge: Complete all formalities as required for study completion (iv) Skip week 4 or week 8 end point evaluation within 2 weeks of DISCHARGE

The total study period is 12 weeks; Primary Efficacy is 'Clinical Recovery' as described in the protocol; Study participant developing severe COVID 19 or severe complication and requiring special critical support/ ICU/ ventilator support will be withdrawn from the study but followed up to record outcome;

Both Ayurvedic and Allopathic Physicians will jointly examine and monitor study participants in addition to the hospital treating physician

Fig 1: Study Flow Diagram with Schedule of Important Study Events

i. Eligibility:

A) Inclusion Criteria:

- i. Typical clinical presentation of acute onset febrile illness with cough and a RT_PCR based laboratory confirmation test for COVID-19
- ii. Patients with either sex, 18 to 75 years age

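### Adjunct trial, section m: investigator withdrawal can rest on a ground only the add-on arm can meet, and outcome recording after withdrawal is stated only for severe cases, so primary outcomes may be missing unequally and informatively

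*Protocol*

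**What the plan says.** All references are to the adjunct-treatment synopsis in the Protocol.

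- **Section m, Withdrawal Criteria.** After allowing the patient to withdraw at any time, it continues: "The investigator may also withdraw the patient due to reasons connected with the severity of disease, interventional drug (adverse event) or some protocol deviation". It then refers the reader elsewhere: "Detailed description is provided in the protocol". That fuller text is not in the document at hand.
- **Fig 1 note.** Patients who develop severe disease or need critical support "will be withdrawn from the study but followed up to record outcome".
- **Section j, secondary outcome 8.** "Safety would also be assessed in case of all withdrawals". Efficacy outcomes are not mentioned there.
- **Section f, Study design.** "This is a prospective, randomized, open label, blinded end point (PROBE), parallel efficacy, multicentric, two arm study". On the arms: "The Ayurveda drug is being considered as an adjunctive or an add-on therapy". The control arm receives SOC alone. The Ayurvedic drug runs for 12 weeks (section e).
- **Section j, primary outcomes.** These are the mean time from randomisation to clinical recovery and the proportion recovering. Recovery must be sustained for at least 48 hours under observation and is rated by a physician blinded to allocation.
- **Section n, Statistical statement.** "Both intent-to-treat and per protocol completer analysis will be performed". The sample size is one of convenience, without a power calculation. Significance is set at two-sided p<0.05.

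**The concern.** Section m gives an investigator who knows the allocation a discretionary power to withdraw the patient. One of its three grounds, an adverse event of the interventional drug, cannot occur in a patient on SOC alone. Another, a protocol deviation, has no threshold. It can arise in either arm, although non-compliance with the study drug can arise only in the add-on arm.

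The blinded rating of recovery gives no protection here, because the decision to withdraw comes before the rating and is not blinded. A patient withdrawn before recovery has been observed and sustained for 48 hours has neither a recovery status nor a recovery time. The text provides for recording the outcome after withdrawal under one ground (severe disease) and not under the other two.

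At stake are both planned analyses. Intention-to-treat needs an outcome for everyone randomised. The completer analysis leaves the withdrawn patients out and is unbiased only if leaving is unrelated to recovery or balanced in number and prognosis. A statistical analysis plan can choose an imputation, but it cannot recover outcomes that were never collected. The rule therefore has to be right in the protocol.

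**Working it through.** **Step 1. What the text provides for each ground**

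| Ground in section m | Arms in which it can arise | Stated after withdrawal |
|---|---|---|
| Disease severity | Both | Outcome recorded if the case becomes severe or needs critical support (Fig 1 note); safety assessed (section j) |
| Interventional-drug adverse event | Add-on only | Safety assessed; no outcome recording stated |
| Protocol deviation | Both; study-drug non-compliance in add-on only | Safety assessed; no outcome recording stated |

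The imbalance in possible grounds follows from the design and needs no assumed rate. The size of any effect does need one.

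**Step 2. Illustration**

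The plan states no withdrawal rate, recovery rate or power, so it has no figure to reproduce.

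Inputs:
- 70 per arm (section g).
- Assumed: true recovery of 80% in both arms, that is 56/70, so the true difference is 0.
- Assumed: 7 add-on patients (10%) and no SOC patient withdrawn before recovery, with no outcome recorded afterwards.
- k = the number of those 7 who would have recovered.

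Formulas for the add-on arm:
- Completers: (56 - k)/63.
- Withdrawn counted as failures: (56 - k)/70.
- SOC is 56/70 = 80.0% in both.

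| Recovery among the 7 | k | Completers | Difference | Counted as failures | Difference |
|---|---|---|---|---|---|
| None | 0 | 56/63 = 88.9% | +8.9 | 56/70 = 80.0% | 0 |
| Half the average (40%) | 2.8 (expected) | 53.2/63 = 84.4% | +4.4 | 53.2/70 = 76.0% | -4.0 |
| Average (80%) | 5.6 (expected) | 50.4/63 = 80.0% | 0 | 50.4/70 = 72.0% | -8.0 |
| All | 7 | 49/63 = 77.8% | -2.2 | 49/70 = 70.0% | -10.0 |

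**Step 3. Effect on the test, second row**

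SE = sqrt(0.844 × 0.156/63 + 0.80 × 0.20/70) = 0.066, so z is shifted by 0.044/0.066 = 0.67. The two-sided 5% test then rejects a true null about 10% of the time.

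**Step 4. Sensitivity to the assumptions**

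With the withdrawn recovering half as often as average:
- True recovery 70% to 90%, withdrawal 10% versus 0%: completers +3.9 to +5.0 points (rejection rate about 8% to 20%); counted as failures -3.5 to -4.5 points.
- True recovery 80%, withdrawal 5% versus 0%: +2.1 and -2.0 points.
- True recovery 80%, withdrawal 15% versus 0%: +7.1 and -6.0 points.
- Withdrawal 5% in both arms with the same prognosis: 0 in both analyses.

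**Step 5. With outcomes recorded on all 140 patients**

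56/70 versus 56/70 gives a difference of 0, whatever k is.

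**The case against.** The strongest objection is that section m is a two-sentence summary that points to a detailed withdrawal description we cannot see. That description may already separate stopping drug from leaving the study and may provide outcome follow-up for everyone. This stands as a limit on the finding. The synopsis still states the grounds and the follow-up as described, and the two texts need to agree.

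Several stronger readings are tempting, and the document does not support them:

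- *Withdrawal falls almost only on the add-on arm, so the arms will be depleted unequally.* Severity and many deviations, such as taking other Ayurvedic products or joining another trial, can arise under SOC. The power is permissive and no rates are given. Unequal loss is a risk, not an established result.
- *Harms in withdrawn patients go unrecorded.* Section j says safety is assessed in all withdrawals. It does not say for how long, but the gap shown here concerns the efficacy outcome.
- *The rule moves a zero difference anywhere from -10 to +8.9 points.* Those two ends come from different analyses and must not be joined into one range.
- *Any deviation over the 12 weeks of drug damages the primary outcome.* Patients are assessed daily until discharge. Once recovery has been recorded, a later withdrawal cannot remove it and affects only later outcomes.

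Two further points stand in part. The +8.9 end requires that none of the seven would have recovered; patients who fail by becoming severe are the ones whose outcome is followed. The trials are also declared exploratory and unpowered, which lowers the stakes. Even so, section n sets a significance level and expects meaningful conclusions.

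**Conclusion.** The point holds as a risk written into the protocol. In an open-label trial the investigator may withdraw a patient on a ground that only one arm can meet, or for an undefined deviation. Outcome recording is then stated for neither. For patients withdrawn before clinical recovery, this can leave primary outcomes missing unequally and informatively.

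Size and direction are unknown. Under the assumptions of 80% recovery in both arms and 10% versus 0% withdrawn before recovery, the completer difference lies between -2.2 and +8.9 points. Counting the withdrawn as failures gives 0 to -10 points. Completer bias vanishes if withdrawal is unrelated to recovery, and bias vanishes in both analyses if withdrawal is equal with the same prognosis.

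The conclusion also assumes that withdrawing a patient in section m means leaving the study. The preceding sentence and the Fig 1 note suggest this, but section m does not say so outright. The change should be made; confidence is medium because the detailed withdrawal text is not shown.

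**What to change.** 1. In section m, separate stopping study drug from leaving the study. When study drug is stopped stays under the existing clinical rules; nothing here changes them.
2. Delete protocol deviation as a ground for leaving the study. Record deviations and handle them in the definition of the per-protocol set.
3. Extend the outcome follow-up in the Fig 1 note to every randomised patient in both arms, unless consent is withdrawn. It should cover the blinded recovery assessment and the scheduled visits to week 12.
4. Make the detailed withdrawal section to which section m refers agree with this.

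The cost is a few sentences in section m and the Fig 1 note, and the effort of following the patients concerned on visits that the schedule already contains.
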